Study objectives and endpoints:	
Primary objective To compare the accuracy and reproducibility of radiation therapy (RT) with open face masks and surface-scanning (SS), and with SS alone without masks to irradiation with a full thermoplastic mask, for patients with head and neck cancer.
 
Primary endpoint Set-up and treatment accuracy, determined by in-vivo dosimetry using PerFRACTION, and by the evaluation of intrafractional motion by comparing a CBCT before and at the end of treatment in patients receiving RT with an open mask, without a mask and using a closed thermoplastic mask.
 
Secondary objectives
 
 1) to demonstrate that irradiation with open face masks and SS or no face masks and SS for patients with head and neck cancer reduces the patients' levels of distress when compared to irradiation with full thermoplastic masks. 2) to demonstrate that irradiation with open face masks and SS or no face masks and SS is feasible for the treating RTT's. 
Secondary endpoints
 
 1) Level of distress of patients, determined by using the subjective units of distress scale (scale of 0-100). 2) Preferred delivery technique as evaluated by treating RTT's involved in this study.
Study design:	Non randomised clinical interventional study
Planned sample size:	In total, 24 patients will be enrolled into this study.

Medical condition or disease under investigation:	Adult HNC patients receiving radiation therapy as their primary treatment
Participant selection criteria:	
Each potential subject must satisfy all of the following criteria to be enrolled in the study.
 
 - Patients \geq 18 years old - Histologically confirmed head and neck cancer. - Patients treated with RT as primary treatment. - An Eastern Cooperative Oncology Group (ECOG) Performance Status grade of 0-1. - Each subject must sign an informed consent form (ICF) indicating that he understands the purpose of and procedures required for the study and is willing to participate in the study. - Patients must be willing to comply with treatment plan and other study procedures. 
Each potential subject must NOT have any of the following criteria to be enrolled in the study.
 
 - Patients with significantly altered mental status or with psychological, familial, sociological or geographical condition potentially hampering compliance with the study. - Individual deprived of liberty or placed under guardianship. - Patients who cannot stay still during fraction because of a disorder (e.g. Parkinson's disease)
Treatment:	
The treatment of every patient will be divided into different phases:
 
 -patients will be irradiated with an open face mask and SS -patients will be irradiated with SS without a mask -patients will be irradiated with a full thermoplastic mask 
The delivery technique will change for every patient each 5 fractions. The first 8 patients included in the study will have the following schedule: full mask-open mask-no mask-full mask-...
 
The 9th till 16th patient included in the study will have the following schedule: open mask-no mask-full mask-open mask-...
 
The 17th till 24th patient included in the study will have the following schedule: no mask-full mask-open mask-no mask-...

Duration of study:	12 months
Accuracy:	
 - In-vivo dosimetry using PerFRACTION - Evaluation of intrafractional motion by comparing a CBCT before and at the end of treatment
Statistical methods:	A sample size of 24 patients is estimated to provide 95% power in order to rule out an mean displacement in excess of 2 mm, assuming a significance level of 0.05 (1-sided as testing for non-inferiority).

	
Mean displacements and standard deviations will be compared for the different delivery techniques for each patient. Using the method described by van Herck, population mean displacement (MD), systematic (R) and random (r) errors were estimated.
 
CBCT registration results will be analysed in 3-dimensions for each patient; population MD, R and r will be calculated. Paired t- tests will be used to compare the parameters listed above, and timing data (CT and treatment session times).
 
Patient comfort and acceptability questionnaires will be summarised as patient comfort scores ranging from 0 (most comfortable) to 100 (least comfortable).
 
RTT satisfaction questionnaires will be summarised as scores ranging from 0 (most satisfactory) to 100 (least satisfactory).
 
Statistical analyses will be performed using SPSS Statistics.

Trial registration:	This study will be registered on www.clinicaltrials.gov

Funding Source: PENDING

KOM OP TEGEN KANKER, PSYCHOSOCIALE COMMISSIE

ADMINISTRATIVE STRUCTURE

Study responsible physician	
[name] Radiotherapeut-oncoloog Iridium Kankernetwerk, gastprofessor Universiteit Antwerpen [contact], [contact] [contact]

Investigator(s)	
[name] Radiotherapeut-oncoloog Iridium Kankernetwerk [contact], [contact] [contact]
 
[name] Radiotherapeut-oncoloog Iridium Kankernetwerk [contact], [contact] [contact]
 
[name] Radiotherapeut-oncoloog Iridium Kankernetwerk [contact], [contact] [contact]
 
[name] Radiotherapeut-oncoloog Iridium Kankernetwerk [contact], [contact]

	
[contact]
 
[name] Radiotherapeut-oncoloog Iridium Kankernetwerk [contact], [contact] [contact]
 
[name] Medical student, University of Antwerp
 
[name] Medical student, University of Antwerp
 
[name] Medical student, University of Antwerp
 
[name] RTT, hoofdverpleegster [contact]
 
[name] RTT [contact]
 
[name] Physicist, Iridium Kankernetwerk [contact], [contact] [contact]
 
[name] Physicist, Iridium Kankernetwerk [contact], [contact] [contact]
 
[name] PhD student
 
[name] PhD student [contact]

Data center	CTO GZA

Sponsor	GZA vzw, [name] [contact], [contact] www.gza.be
----------------	--

1. Introduction

1.1 Background & rationale

Head and neck cancer (HNC) is a broad term that encompasses a large number of tumour entities originating from different subsites, such as the nasal cavity, nasopharynx, oral cavity, oropharynx, larynx, hypopharynx and salivary glands.

In Belgium, in the year 2016 (latest data Belgian Cancer Registry), more than 2500 patients were diagnosed with head and neck cancer. (1) In the United States, for the year 2014, there was an estimate of 55.070 new cases of HNC (2). Approximately 60% to 80% of HNC patients present with loco-regionally advanced disease at time of diagnosis. The main treatment options for loco-regionally advanced HNC are (chemo-) radiotherapy (RT) and surgery (often followed by RT). During each RT course, patients are immobilised using a thermoplastic mask (**Figure 1 a.**) to limit the possibility to move during the treatment. Furthermore, this mask enables correct positioning before the start of each RT session.

[figure not shown]

Figure 1. Full thermoplastic mask (a.) and open thermoplastic mask (b.).

The use of these masks results in the following disadvantages:

- They can cause claustrophobia and anxiety. (3, 4, 6)
- Intrafractional surface monitoring is not possible with closed masks. (3)
- Full-face masks can be very uncomfortable and cause pain by pressure. (5, 6, 7)
- The masks don't adapt to weight loss or edema that can occur during radiotherapy.

Lately, to reduce these side effects, there is an interest in using open face masks (**Figure 1 b.**) in combination with surface scanning (SS). SS is a system which tracks a patient's position before and during RT, to aid in setup and treatment accuracy. Using 3D stereo camera units, the SS tracks the skin surface, and compares it to the ideal position. (4) The combination of an SS and an open face mask therefore enables us to monitor intrafractional movement. (8) This system can then automatically signal the treatment delivery system to pause radiation if the patient moves out of the desired position.

The use of SS together with open face masks for HNC has been studied. An overview of the relevant literature review can be found in **Table 1**.

Article	Number of participants	Hypothesis	Conclusion
A prospective evaluation of open face masks for head and neck radiation therapy. Wiant D, Squire S, Liu H, Maurer J, Lane Hayes T, Sintay B.	50	To investigate if open mask radiotherapy can be implemented as the new standard for the treatment of HNC.	Immobilization with an open mask works as well as with a closed mask and offers the possibility of real-time monitoring with surface scans.
Migration from full-head mask to "open-face" mask for immobilization of patients with head and neck cancer. Li G, Lovelock DM, Mechalakos J, Rao S, Della-Biancia C, Amols H, et al.	15	To quantitatively characterize the immobilization performance of the open-face mask.	Open-face masks offer advantages in patient comfort and can be used in the treatment of head and neck cancer.
Minimal mask immobilization with optical surface guidance for head and neck radiotherapy. Zhao B, Maquilan G, Jiang S, Schwartz DL.	20	To investigate the feasibility and setup accuracy of minimal face and neck mask immobilization with optical surface guidance.	Minimal mask immobilization offers a streamlined clinical workflow with surface guidance during set-up and treatment. On-board radiographic imaging remains the recommended standard.

Table 1. Relevant literature concerning the use of open-face masks and OSMS

Until now, 3 studies have investigated the use of open face masks in combination with SS. Although the results of these studies are promising, even open masks can be problematic for claustrophobic patients or patients with edema or weight loss during RT. Theoretically, it should be possible to combine a less-rigid immobilization with continuous patient motion monitoring to minimize patient discomfort, without losing precision of the treatment (9). Therefore, we want to test the feasibility of irradiating head and neck cancer patients without a mask using SS and compare this technique with open face masks and full thermoplastic masks. The results of this study could possibly help us find a proper alternative for patients who have difficulties with full and open masks. Until now, maskless irradiation has only been investigated in one study with whole brain irradiation (6), so more research is definitely necessary.

In the future, the knowledge we gather with this study regarding SS and maskless irradiation in head and neck cancer patients, will help us to set up new studies eg. the introduction of precise stereotactic radiotherapy for head and neck cancer patients.

1.2 Risks and benefits

- **Possible risk:**

A longer treatment time in the open face mask or mask-less phase

- **Possible benefit:**

-Possibly less claustrophobia in the open face mask or mask-less phase

2. Overall study design

The study is designed to evaluate whether irradiating head and neck cancer patients without a mask or with open face masks using SS is comparable to irradiation with full thermoplastic masks in terms of set-up and treatment accuracy and average treatment time.

In total, 24 patients will participate in the study. They are treated with radiotherapy for 35 fractions.

The treatment of every patient will be divided into different phases:

- patients will be irradiated with an open face mask and SS
- patients will be irradiated without a mask but with SS
- patients will be irradiated with a full thermoplastic mask

The delivery technique will change for every patient each 5 fractions.

- The first 8 patients included in the study will have the following schedule:
full mask-open mask-no mask- full mask-open mask-no mask-full mask
- The 9th till 16th patient included in the study will have the following schedule:
open mask-no mask-full mask-open mask-no mask-full mask-open mask
- The 17th till 24th patient included in the study will have the following schedule:
no mask-full mask-open mask- no mask- full mask-open mask-no mask

We chose the number of patients for each group based on the published literature and the power calculation (Table 1).

2.1 Study period

For each participant, the study starts once written consent is provided and is composed by 2 study phases.

Screening phase

Eligibility of patients will be determined according to the inclusion/exclusion criteria as detailed in section 8. Patients are asked complete the validated Dutch claustrophobia questionnaire before start of treatment (see Section 12 and appendix 1).

Treatment phase

Once enrolled, fully eligible patients will start the intended RT according to the standard of care. The RT dose prescription is left to the discretion of the treating radiation oncologist and is the current standard treatment. Patients are asked about their distress level by the treating physician on a weekly basis (see Section 12 and appendix 2). A score of 0-100 is given by using the Subjective Units of Distress Scale.

The set-up and treatment accuracy will be determined by in-vivo dosimetry using PerFRACTION and by the evaluation of intrafractional motion by comparing a CBCT before and at the end of treatment.

The average treatment time will be measured for all treatment fractions.

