3.3 Secondary objective

Our secondary objective is:

- 3) to demonstrate that irradiation with open face masks and SS or no face masks and SS for patients with head and neck cancer reduces the patients' levels of distress when compared to irradiation with full thermoplastic masks.
- 4) to demonstrate that irradiation with open face masks and SS or no face masks and SS is feasible for the treating RTT's.

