3.4 Secondary endpoints

- 3) Level of distress of patients, determined by using the subjective units of distress scale (scale of 0-100).
- 4) Preferred delivery technique as evaluated by treating RTT's involved in this study.

Our hypothesis for this trial can be best described by the PICO (Patient Intervention Comparison Outcome):

- Patient: patients who are in need of primary treatment with radiotherapy for a histologically confirmed HNC
- Intervention: irradiation with SS and an open face mask; irradiation with SS but without a thermoplastic mask
- Comparison: standard of care treatment, irradiation with a full thermoplastic mask
- Outcome: accuracy of the irradiation (in-vivo dosimetry, intra-fractional motion during radiotherapy); duration of the irradiation in the different groups; results of claustrophobia questionnaires; results of RTT satisfaction questionnaires

4. Study population

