7.2 Study procedures

The study procedures are described in subsequent sections

Patient demographics and other screening characteristics

The data that will be collected at screening include:

- Demography (date of birth)
- ECOG performance status (Appendix 3)
- Patient questionnaire: the Dutch Claustrophobia questionnaire
- Use of anxiolytic medication

Accuracy assessments

- using PerFRACTION (in vivo dosimetry)
- using the intrafractional motion determined by the change in position between the CBCT pre and post treatment

Assessment of patients' distress level

-Weekly using the level of distress (see appendix)

Assessment of treatment time

-Will be done automatically using the radiotherapy delivery software

Assessment of RTT preference

- Using score of 0-100

8. Safety monitoring and reporting

ICH GCP and the EU Directive 2001/20/EC require that both investigators and sponsors follow specific procedures when notifying and reporting adverse events/reactions in clinical trials. These procedures are described in this section of the protocol.

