Appendix 1: Dutch Claustrophobia questionnaire (English translation)

Name:.....

Date.....

[figure not shown]
How anxious would you feel in the following situations?

A= Not anxious B= a bit anxious C=Fairly anxious D= very anxious E= Extremely anxious

1. Being restrained in a straight jacket for 15 minutes.
2. Being tied to an immovable chair.
3. Being tied up with your hands behind your back for 15 minutes.
4. Being handcuffed for 15 minutes
5. Being locked up in a small dark room during 15 minutes
6. Laying in a small sleeping bag which fits tightly around your arms and legs and which is tied at the level of your neck.
7. Laying in the trunk of a car during 15 minutes with sufficient oxygen supply.
8. Wearing clothes that are too small and not being able to remove them.
9. Laying in a closed sleeping bag with your head at the end where your feet should be and not being able to get out.
10. Being locked up in a lit room without windows for 15 minutes.
11. Being in an overcrowded train, stopped between two stations.
12. Noticing the door is jammed on a public toilet.
13. Swimming with a nose clip on.
14. Working underneath the sink for 15 minutes.
15. Standing in an elevator on the ground floor with the doors shut.
16. Trying to catch your breath during heavy exercise.
17. Having trouble breathing through your nose during a bad cold.
18. Snorkeling in a safe practice tank for 15 minutes.
19. Using an oxygen mask.
20. Lying at the bottom of a bunk bed
21. Standing on the third row at a sold-out concert and realizing you won't be able to leave the room before the end of the show.
22. Sitting in the middle of a full row at the movie theater.
23. Working beneath a car for 15 minutes.
24. Standing still during an excursion within an underground mine at the furthest point from the exit.
25. Lying inside a sauna for 15 minutes.
26. Waiting inside of an airplane which stands on the ground while the doors are closed.

The distress thermometer – Subjective Units of Distress Scale (SUDS)

Try to get used to rating your distress, fear, anxiety or discomfort on a scale of 0-100. Imagine you have a 'distress thermometer' to measure your feelings according to the following scale. Notice how your level of distress and fear changes over time and in different situations.

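### Distress is rated weekly with no link to a session while the technique changes every 5 fractions, so part of a rating can describe the previous technique and shrink the full-minus-open difference

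*Combined protocol and SAP*

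**What the plan says.** The secondary objective in Section 3.3 is a comparison between techniques: to show that open mask or no mask with surface scanning "reduces the patients' levels of distress when compared to irradiation with full thermoplastic masks". The measure is the 0-100 Subjective Units of Distress Scale (SUDS).

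On collection, Section 2.1 says "Patients are asked about their distress level by the treating physician on a weekly basis". Section 7.2 and Table 2 also give only a weekly frequency. The scale text in the appendices tells the patient: "Notice how your level of distress and fear changes over time and in different situations". It gives no recall period and does not mention a treatment session.

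On treatment, Section 2 says "The delivery technique will change for every patient each 5 fractions" and "They are treated with radiotherapy for 35 fractions", which makes 7 phases of 5. The first 8 patients follow "full mask-open mask-no mask- full mask-open mask-no mask-full mask". The other two groups enter the same cycle at open mask and at no mask.

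Table 2 does tie other measures to treatment: in-vivo dosimetry and intrafractional motion to the first 3 sessions of each phase, and treatment time to every session. Section 10.2 says that comfort scores will be summarised, but gives no rule for assigning a distress rating to a technique.

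**The concern.** Distress is collected on a calendar clock and the technique changes on a fraction clock. The protocol does not give fractions per week, the weekday of the physician visit, the order of visit and session on that day, or the period the patient should have in mind. A rating taken early in a phase, or before that day's session, can therefore describe the technique just left, in part or in full, while being analysed under the technique now in use.

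In many crossover layouts such error would be partly balanced. Here each technique has the same predecessor in every group, so lagged ratings push the comparison one way. At stake is a real reduction in distress that the trial would understate or miss. A recall window that was never specified cannot be reconstructed after the data are in.

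**Working it through.** **The plan's own figure.** There is none for distress. The 24 patients and 95% power in Section 10.1 concern mean displacement, so nothing is reproduced here.

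**Inputs from the protocol.** 35 fractions, a switch every 5, three sequences of 7 phases with 8 patients each (Sections 2 and 5), and a weekly rating.

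**Assumptions (not in the protocol).** True SUDS of 40 for full mask, 25 for open and 20 for none. So d1 = full minus open = 15 and d2 = full minus none = 20. Five fractions per week.

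**Step 1: order of techniques.** The three sequences contain 3 × 6 = 18 changes of phase: full to open 6, open to none 6, none to full 6. Open always follows full, and full always follows none.

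**Step 2: formula.** Let m be the share of a rating that describes the preceding technique. A patient's first phase has no predecessor. Averaged within patient and then over the three groups, the share of full-mask phases with a predecessor is (2/3 + 1 + 1)/3 = 8/9. It is also 8/9 for open and for none. Hence

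- observed full minus open = d1 − m × (8/9) × (d1 + d2)
- observed full minus none = d2 − m × (8/9) × (2 × d2 − d1)

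**Step 3: values of m**

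- Rating reflects that day's session, asked after it: m = 0 on any fraction.
- Rating reflects the last session, asked before treatment, visit day evenly spread: only a fraction-1 visit lags, so m = 1/5 = 0.2.
- Rating reflects the last 5 fractions, asked after fraction k: m = (5 − k)/5. Evenly spread, m = (0.8 + 0.6 + 0.4 + 0.2 + 0)/5 = 0.4.
- The same recall, asked before fraction k: m = (6 − k)/5. Evenly spread, m = 0.6.

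**Step 4: results**

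| Reading | m | Full minus open (true 15) | Full minus none (true 20) |
|---|---|---|---|
| That day's session, asked after | 0 | 15.0 | 20.0 |
| Last session, asked before, even spread | 0.2 | 15 − 0.2 × 8/9 × 35 = 8.8 | 20 − 0.2 × 8/9 × 25 = 15.6 |
| Last 5 fractions, asked after, even spread or fraction 3 | 0.4 | 2.6 | 11.1 |
| Last 5 fractions, asked after fraction 2, or asked before with even spread | 0.6 | −3.7 | 6.7 |
| Last 5 fractions, asked after fraction 1 | 0.8 | −9.9 | 2.2 |

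The second row is about 8 to 9 because it depends on how the first phase is handled. Ignoring the first phase gives 0.8 × 15 − 0.2 × 20 = 8.0. If the rating reflects the last session and every rating is taken before fraction 1, full is scored 20 and open 40. The difference is then −20, leaving out the first phase.

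**Step 5: when the sign changes.** Setting the first formula to zero gives m = 9 × d1 / (8 × (d1 + d2)). For 15 and 20 this is 135/280 = 0.48. With d1 = 10, it is 0.56 for d2 = 10, 0.375 for d2 = 20 and 0.28 for d2 = 30. For d2 = 0 it is 90/80, above 1, so no reversal is possible. With other assumed scores of 30, 20 and 20, m = 0.4 gives 10 − 0.4 × 8/9 × 20 = 2.9 against a true 10.

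**The case against.** The best defence is that 35 fractions, 7 phases of 5 and a weekly rating fit an intention of one rating per phase. At 5 fractions per week with no lost day, a fixed weekly visit meets the same fraction of every phase whatever the start weekday. A Wednesday start with a Tuesday visit always lands on fraction 5. If the patient is asked after the session and answers for that session, there is no bias. This stands, but the protocol does not secure any of those conditions.

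A dated rating could also be matched to the technique in use that day, since treatment time is logged at every session and Section 11.6 requires attributable, contemporaneous source data. That stands against crediting by calendar week. It does not settle which sessions the patient had in mind.

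Several stronger readings are tempting and are not supported:

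- A reader might infer that the trial will reverse the difference. That requires roughly half or more of the rating to describe the previous technique under the scores assumed here, and all the scores are assumptions.
- A reader might blame a midweek start or a lost day. Neither is the cause as such: a Monday start with a Wednesday visit lands on fraction 3 with nothing lost, and one lost day can move a fraction-1 visit to fraction 5. What matters is the position of the visit in the phase and the recall window.
- A reader might infer that full-mask distress is always credited to open mask. That holds only for ratings that lag. If ratings anticipate the next phase, full minus open can be unchanged (d1 = 10, d2 = 20) or grow (d2 = 30).
- A reader might take the score to be the physician's own. The scale text addresses the patient, so it is a self-rating that the physician elicits.

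The figures in Section 6.1 and the scale figure are not shown, and the Section 12 cited in Section 2.1 is not in the readable text. Timing instructions there cannot be excluded.

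**Conclusion.** The concern holds as a weakness in how distress is collected. On the readable text, a rating is not tied to a session, a before-or-after time or a recall window, and the common cycle makes any lag directional.

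Under assumed scores of 40, 25 and 20, a true full-minus-open difference of 15 would be seen as anything from 15, through about 8 to 9, down to 2.6 under the favourable and moderate readings. A negative difference needs an unfavourable combination: recall over five fractions with visits on fractions 1 or 2, or routinely before the session, or every rating taken before fraction 1 of a phase. Attenuation is the realistic risk and reversal the extreme one.

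The size rests on the assumed scores, on 5 fractions per week and on the assumed recall. The presence of the gap does not. Distress is a secondary endpoint, and the accuracy comparison is not affected.

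**What to change.** In Sections 2.1 and 7.2 and in Table 2, replace the weekly SUDS question with one patient self-rating per phase. Take it at a fixed session late in the phase, for example the last delivered fraction, immediately after treatment and referring to that session. Record the date, fraction number and technique on the form. In Section 10.2, state that each rating is analysed under the technique recorded with it.

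This sets m to 0, and the assumed 15 points are recovered as 15.0. Any fixed post-treatment session with that reference removes the misattribution. A late one also protects against patients who answer for several sessions, but it will not capture distress on first exposure to a technique, so the sponsor should choose knowingly.

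The cost is small. The count is still 7 ratings per patient, 7 × 24 = 168 in all and 56 per technique. The rating moves from the weekly consultation to the treatment session.

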4.3 Subject withdrawal criteria and procedures

- The general condition of the patient is too bad to continue the RT
- The patient can withdraw from the study at any moment for any reason

The patients who withdraw will not be replaced.

Specific aftercare for this therapeutic strategy is no different from the current standard of care.

5. Treatment allocation

Patients will be assigned to a study group based on their date of enrolment.

The treatment of every patient will be divided into different phases:

- patients will be irradiated with an open face mask and SS
- patients will be irradiated without a mask but with SS
- patients will be irradiated with a full thermoplastic mask

The delivery technique will change for every patient each 5 fractions.

[figure not shown]
- The first 8 patients included in the study will have the following schedule:
full mask-open mask-no mask- full mask-open mask-no mask-full mask
- The 9th till 16th patient included in the study will have the following schedule:
open mask-no mask-full mask-open mask-no mask-full mask-open mask
- The 17th till 24th patient included in the study will have the following schedule:
no mask-full mask-open mask- no mask- full mask-open mask-no mask

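### The treating physician asks for the weekly distress score while patient and physician can both see the technique, which exposes the distress comparison to technique-dependent reporting bias that patient self-completion would reduce

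*Combined protocol and SAP*

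**What the plan says.** Section 2.1 (Treatment phase) sets the mode of collection: "Patients are asked about their distress level by the treating physician on a weekly basis". It continues: "A score of 0-100 is given by using the Subjective Units of Distress Scale". The procedure is referred to a Section 12, but the numbered sections end at 11. Sections 7.1 and 7.2 add only that distress is scored weekly.

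The objective in Section 3.3 has a direction. It is to demonstrate that the open mask or no mask "reduces the patients' levels of distress when compared to irradiation with full thermoplastic masks". Section 1.2 names the hoped-for benefit in advance: "Possibly less claustrophobia in the open face mask or mask-less phase".

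The synopsis calls the trial a "Non randomised clinical interventional study", and Section 5 says "Patients will be assigned to a study group based on their date of enrolment". No blinding of patient, physician or assessor is described.

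The scale in the appendices speaks to the patient: "Try to get used to rating your distress, fear, anxiety or discomfort on a scale of 0-100". It does not say that the patient fills it in alone, or who collects it. By contrast, Section 2.1 asks patients to complete the claustrophobia questionnaire themselves, but Table 2 schedules that at screening only.

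**The concern.** The distress score is the only patient-reported measure that Table 2 schedules during treatment, so the claim of reduced distress rests on it. The person asking is the doctor responsible for the treatment. That doctor can see which technique is in use and can know which result the trial hopes for. Patients may shade their answers to suit the doctor, and the doctor may put the question differently from one technique to the next.

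If either effect differs between techniques, it becomes part of the estimated difference and cannot be separated from it after the data are in. Choosing the right day and session for each technique would not remove it, because a well-timed score can still be shaped by who asks. Section 6.2 already records anxiolytic use because it could affect the results. The plan has no comparable protection against the influence of the person asking.

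**Working it through.** **The plan's own figure.** The plan gives no effect size, SD, margin or power for distress. The 24 patients in Section 10.1 are justified for a 2 mm displacement margin. No SD is given there either, and the figure has no bearing on distress.

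**Step 1: what cancels and what does not.** Write patient i's reported score under technique j as

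reported = true score + a_i + b_j,

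where a_i is a reporting shift that is the same under every technique and b_j is a shift that depends on the technique. The within-patient difference between a new technique and the full mask has expectation

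true difference + (b_new − b_full).

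The common shift a_i drops out because each patient receives all three techniques (Section 2). The term (b_new − b_full) stays in full and does not shrink with more patients. Two examples:
- All scores lowered by 5 points: the difference changes by 5 − 5 = 0.
- Scores lowered by 5 points only in new-technique weeks: a true difference of 0 is reported as a 5-point reduction.

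**Step 2: what this would do to a test (illustration).** Inputs:
- From the documents: n = 24, so df = 23.
- Assumed: a paired t-test at two-sided 0.05, true difference zero, a differential bias B of 5 or 3 points towards the new technique, and an SD of paired differences S of 10, 15, 20 or 30 points.

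The noncentrality parameter is B / (S/√24), and the chance of wrongly favouring the new technique is the probability that a noncentral t with 23 df exceeds 2.069. For B = 5 and S = 10, the parameter is 5 × 4.899 / 10 = 2.449.

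| S (points) | Noncentrality, B = 5 | False result, B = 5 | Noncentrality, B = 3 | False result, B = 3 |
|---|---|---|---|---|
| 10 | 2.449 | 65.0% | 1.470 | 29.1% |
| 15 | 1.633 | 34.6% | 0.980 | 15.4% |
| 20 | 1.225 | 21.6% | 0.735 | 10.5% |
| 30 | 0.816 | 12.0% | 0.490 | 6.8% |

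Without bias the rate in this direction is 2.5%.

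**Step 3: effect of the repeated phases.** With 35 fractions in blocks of 5 there are 35 / 5 = 7 phases, so each patient has each technique in two or three of them. Averaging over these phases reduces random variation, and so S, but leaves B unchanged. It therefore gives no protection against the bias.

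**The case against.** **The bias might not favour the new techniques.** This stands. A patient who wants to please the doctor could also play down distress under the full mask, since that is the same doctor's treatment. With a true reduction of 5 points and a 5-point bias the other way, the reported difference would be 5 − 5 = 0. The documents show a risk, not a direction. A reader might infer that the distress result will be biased towards the open mask or no mask, but nothing in the plan establishes that.

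**The error rates rest on assumptions and on a test that is not stated.** This also stands. Section 10.2 says that comfort scores will be summarised, and it assigns paired t-tests to displacement parameters and timing data before it mentions the questionnaires. It would be wrong to read 65% as this trial's error rate: it belongs to the smallest SD shown, an assumed bias and a hypothetical test. Step 1 does not depend on any of these, because a summary of mean differences is shifted just as a test would be.

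**The asker need not be an investigator.** A reader might infer that a committed investigator takes the score. The administrative structure lists 5 radiation oncologists among 14 investigators, plus the study responsible physician, and the documents do not say whether the treating physician is one of them. The point needs only that the treating physician asks and can see the technique.

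**The text may allow the patient to mark the scale.** A physician could hand over the scale, and the plan uses neither the term face to face nor the term unblinded. Both are inferences from the wording and from the visible masks. But Section 2.1 names the physician as the one who asks, and no other section provides for completion by the patient. The objection supports stating the mode clearly; it does not remove the exposure.

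**Self-completion leaves patients unblinded.** True. They see and feel the mask, so their own expectation remains. The change reduces only the part due to being asked by the doctor.

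**Conclusion.** The concern holds as a risk to one secondary endpoint. The plan states a way of collecting distress that lets technique-dependent reporting enter the comparison, although its own scale is worded for self-rating. Any such part adds point for point to the difference, and neither the crossover nor the number of patients removes it.

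Its size and direction are unknown. Under the assumptions above, a 5-point bias would raise the false-positive rate in favour of the new technique from 2.5% to between 12% and 65% over SDs of 30 down to 10 points, and a 3-point bias to between 7% and 29%. These figures show that a modest bias matters with 24 patients; they do not estimate what will happen here. The displacement, dosimetry and treatment-time comparisons are not affected.

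**What to change.** Change Sections 2.1 and 7.2 so that the patient marks the 0-100 distress scale on paper or tablet before the weekly contact with the physician. The form carries the participant number and the current technique and is collected by existing clinic staff. Flag any score that was obtained verbally, and repeat the distress comparison without the flagged scores. State as a limitation that patients know their technique, so their own expectation can still influence the ratings. The same edit can correct the reference to Section 12.

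The cost is a short text change, a one-item form each week and some missed forms. The physician may see and discuss the score afterwards as usual, so no score is withheld and no extra staff are needed. The change must be made before data collection, because how a score was obtained cannot be altered afterwards.
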